8.2 Secondary, Exploratory Efficacy Endpoints and Analyses

Key Secondary Endpoints:

The 3 endpoints immediately following this paragraph will be tested by using a fixed sequence procedure to protect the familywise error rate at 0.05. If the primary outcome measure is statistically significant, the p-values of the secondary measures will be examined in the order listed below. The process stops at the first p-value above 0.05.

- Responder rate (experiencing a $\geq 50\%$ reduction) during the titration + maintenance treatment periods of the DB phase for Cohort 2
- Change in the number of seizure free days per 28-day period from baseline during the titration + maintenance treatment phases of the DB phase for Cohort 2

Clinical Global Impression of Change – Improvement (CGI-I; Investigator) at Week 14 of the double blind treatment phase relative to the baseline for Cohort 2. All remaining secondary efficacy endpoints listed in the protocol will be tested at $\alpha = .05$ so all p-values are nominal.

Secondary efficacy outcome measures are listed below.

- a) Percent change in the 28-day seizure frequency from baseline to the DB phase during the maintenance treatment phase for Cohort 2
- b) Change from baseline in 28-day seizure frequency during the DB phase for Cohort 2 (titration + maintenance and maintenance only)
- c) Change in the number of seizure free days per 28-day period from baseline during the maintenance treatment phase of the DB phase for Cohort 2
- d) Proportion of responders experiencing a $\geq R\%$ reduction from baseline to the end of treatment period in 28-day seizure frequency (titration + maintenance and maintenance only) for Cohort 2. R% will be 20%, 40%, 60%, and 80%
- e) Proportion of subjects who completed the DB portion of the study (Cohort 2) and did not experience any seizures during the maintenance phase of the study
- f) Proportion of subjects who experienced at least one 28-day seizure free period during the DB phase of the study (titration + maintenance) for Cohort 2
- g) Longest period of time seizure free (%) (longest period of seizure free days divided by number of days with available seizure data) during the double blind phase (titration + maintenance) for Cohort 2
- h) Change from baseline in 28-day seizure frequency for different subtypes of seizures during the DB portion of the study (titration + maintenance) for Cohort 2 (SPS, SPS-motor, CPS, SGTC)
- i) Patient Global Impression of Change – Improvement (PGI-I; Patient/Caregiver) at each assessment visit
- j) Clinical Global Impression of Change – Improvement (CGI-I; Investigator) at each assessment visit

Exploratory endpoint

[REDACTED]

[REDACTED] except that the primary endpoint and 50% responder rate will be analyzed the same way as in Cohort 2.

The other primary and secondary efficacy outcome measures will be assessed descriptively for the time periods listed below in Cohort 1 DB phase ([a-e] below) and Cohort 1 + Cohort 2 OL ([f below]):

- a) Ganaxolone Titration + Maintenance 1200 mg/day + Maintenance 1800 mg/day vs Placebo (Cohort 1: Weeks 1 to 9).

- b) Ganaxolone Maintenance 1200 mg/day + Maintenance 1800 mg/day (Cohort 1: Weeks 2-9) vs Placebo (Cohort 1: Weeks 1 to 9).
- c) Ganaxolone Titration + Maintenance 1200 mg/d (Cohort 1: Weeks 1-5) vs placebo (Cohort 1: Weeks 1 to 9).
- d) Ganaxolone Maintenance 1800 mg/d (Cohort 1: Weeks 6-9) vs placebo (Cohort 1: Weeks 1 to 9).
- e) Ganaxolone maintenance 1200 mg/d vs placebo (Cohort 1: Weeks 2 to 5).
- f) OL (Cohort 1: Weeks 10 to 61; Cohort 2: Weeks 16 to 66).

8.2.2 Change from Baseline in 28-day Seizure Frequency and Change from Baseline in 28-day Seizure Frequency for different subtypes of seizures (SPS, SPS-motor, CPS, SGTC)

A rank analysis of covariance (ranked ANCOVA) will be performed. A nonparametric rank analysis of covariance will be used to analyze rank of change from baseline in 28-day seizure frequency, with treatment and pooled center (either US or ROW) as factors and the rank of baseline 28-day seizure frequency as a covariate in the model. The baseline, post-baseline, and change from baseline in 28-day seizure frequency will be summarized by treatment group by using descriptive statistics. The 95% confidence interval of the median by treatment group will also be presented. The 2-sided significance level of 0.05 will be used for comparison. Hodges–Lehmann estimator of the difference in medians together with 95% confidence interval (CI) will be calculated.

Summary table with descriptive statistics will be provided in OL phase for Cohort 1,2, and the combined 2 cohorts. The baseline is the same as for the DB phase.

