- j) Clinical Global Impression of Change – Improvement (CGI-I; Investigator) at each assessment visit

Exploratory endpoint

[REDACTED] except that the primary endpoint and 50% responder rate will be analyzed the same way as in Cohort 2.

The other primary and secondary efficacy outcome measures will be assessed descriptively for each of the time periods listed below in Cohort 1 DB phase ([a-e] below) and Cohort 1+Cohort 2 OL ([f below]):

- a) Ganaxolone Titration + Maintenance 1200 mg/day + Maintenance 1800 mg/day vs Placebo (Cohort 1: Weeks 1 to 9).
- a) Ganaxolone Maintenance 1200 mg/day + Maintenance 1800 mg/day (Cohort 1: Weeks 2-9) vs Placebo (Cohort 1: Weeks 1 to 9).
- b) Ganaxolone Titration + Maintenance 1200 mg/d (Cohort 1: Weeks 1-5) vs placebo (Cohort 1: Weeks 1 to 9).
- c) Ganaxolone Maintenance 1800 mg/d vs (Cohort 1: Weeks 6-9) placebo (Cohort 1: Weeks 1 to 9).
- d) Ganaxolone maintenance 1200 mg/d vs placebo (Cohort 1: Weeks 2 to 5).
- e) OL (Cohort 1: Weeks 10 to 61; Cohort 2: Weeks 16 to 66).

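### Three exploratory Cohort 1 comparisons in the SAP set a shorter ganaxolone window against placebo Weeks 1-9; the protocol uses one week range per comparison, and SAP section 10 does not record the change

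*SAP*

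**What the plan says.** SAP section 8.2 introduces the Cohort 1 period comparisons with "The other primary and secondary efficacy outcome measures will be assessed descriptively for the time periods listed below in Cohort 1 DB phase". Three of the five double-blind comparisons that follow give each arm its own weeks:

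- For both dose levels together, the item reads "Ganaxolone Maintenance 1200 mg/day + Maintenance 1800 mg/day (Cohort 1: Weeks 2-9) vs Placebo (Cohort 1: Weeks 1 to 9").
- For titration plus the lower dose, it reads "Ganaxolone Titration + Maintenance 1200 mg/d (Cohort 1: Weeks 1-5) vs placebo (Cohort 1: Weeks 1 to 9").
- For the higher dose alone, it reads "Ganaxolone Maintenance 1800 mg/d (Cohort 1: Weeks 6-9) vs placebo (Cohort 1: Weeks 1 to 9").

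SAP section 4.2 carries the same three. Its item for both dose levels together reads "a) Ganaxolone Maintenance 1200 mg/day + Maintenance 1800 mg/day (Cohort 1: Weeks 2-9) vs Placebo (Cohort 1: Weeks 1 to 9"). Its item for titration plus the lower dose reads "b) Ganaxolone Titration + Maintenance 1200 mg/d (Cohort 1: Weeks 1-5) vs placebo (Cohort 1: Weeks 1 to 9"). Its item for the higher dose alone reads "Ganaxolone Maintenance 1800 mg/d vs (Cohort 1: Weeks 6-9) placebo (Cohort 1: Weeks 1 to 9"). The repetition makes a slip in one list an unlikely explanation.

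The SAP is not uniform. The 1200 mg/d maintenance item has a single range for the whole comparison: "Ganaxolone maintenance 1200 mg/d vs placebo (Cohort 1: Weeks 2 to 5").

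The protocol (section 9.7.6 and the synopsis) gives one range per comparison: Weeks 2-9, Weeks 1-5 and Weeks 6-9 for the three items above. SAP section 10, which is meant to record departures from the protocol, has one entry, on restricting the primary efficacy analysis to Cohort 2. The available SAP text gives no reason for the longer placebo window.

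**The concern.** When the arms are observed over different weeks, a difference between them can come from treatment, from the length of the window or from the time on study at which it falls. Several of the listed outcomes depend on window length by construction. These are the responder cut-offs, the longest seizure-free stretch as a percentage of observed days, and the occurrence of any 28-day seizure-free period.

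The practical risk lies in reading across dose levels. The 1800 mg/d maintenance row compares 28 days with 63, and the 1200 mg/d maintenance row compares 28 with 28. A reader who sets the two rows side by side to judge dose response sees a built-in difference on some measures even if the drug does nothing. At stake is the interpretation of exploratory tables, not the trial's conclusions.

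**Working it through.** The plan states no figure to reproduce here. The check is a comparison of the two texts, followed by an estimate of what the mismatch does.

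**1. Windows.** Day ranges follow the Cohort 1 dosing table in protocol section 9.4.5: days 1-7 titration, 8-35 at 1200 mg/d, 36-63 at 1800 mg/d.

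| Comparison | Protocol weeks | SAP ganaxolone | SAP placebo | Placebo days outside the ganaxolone window |
|---|---|---|---|---|
| 1200 + 1800 mg/d maintenance | 2-9 | 56 days | 63 days | 7/63 = 11.1%, earlier |
| Titration + 1200 mg/d maintenance | 1-5 | 35 days | 63 days | 28/63 = 44.4%, later |
| 1800 mg/d maintenance | 6-9 | 28 days | 63 days | 35/63 = 55.6%, earlier |
| 1200 mg/d maintenance | 2-5 | 28 days | 28 days | 0 |

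**2. Why length matters without any drug effect.** For a Poisson count at rate λ, the observed rate over d days has variance λ/d. Going from 63 days to 28 multiplies the variance by 63/28 = 2.25 and the standard deviation by 1.5, so more subjects cross a distant responder cut-off by chance. A run of 28 seizure-free days has 63 − 28 + 1 = 36 possible start days in the long window and one in the short.

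**3. Size under assumed rates.** The documents give no seizure-rate distribution, so nine scenarios were simulated, with 60,000 eligible subjects each:

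- The 28-day rate is lognormal with median 6, 10 or 15 and log-SD 0.8.
- Daily counts are Poisson with a weekly gamma multiplier of shape infinity (pure Poisson), 2 or 0.7.
- The 56-day baseline has 3 to 100 seizures in each 28 days and no seizure-free run over 21 days.
- The true rate is constant over 63 days at 1, 0.898 or 0.74 times baseline. The last two use the median reductions of 10.2% (placebo) and 26% (ganaxolone) that protocol section 7 reports for study 1042-0600.

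Results for Weeks 6-9 minus Weeks 1-9, in percentage points, as ranges over the nine scenarios:

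| Responder cut-off | No change | 10.2% reduction | 26% reduction |
|---|---|---|---|
| ≥20% | +5.2 to +6.9 | +3.3 to +5.5 | −1.6 to +2.2 |
| ≥40% | +4.6 to +9.4 | +6.2 to +8.6 | +4.6 to +7.0 |
| ≥60% | +1.9 to +11.3 | +2.7 to +11.2 | +5.2 to +10.4 |
| ≥80% | +0.4 to +7.8 | +0.6 to +8.9 | +1.3 to +10.1 |

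Other measures with no change from baseline:

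- Mean longest seizure-free stretch: +8.1 to +14.6 points.
- Any 28-day seizure-free period: −0.6 to −9.5 points.
- Mean change in 28-day frequency and in seizure-free days: within 0.1.
- Median change in 28-day frequency: −1.2 to +0.1 seizures.

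One scenario in full (median 10, shape 2, no change), Weeks 6-9 against Weeks 1-9: ≥40% responders 24.1% v 15.5%; ≥60% 10.6% v 3.6%; longest stretch 29.7% v 18.4%; any 28-day seizure-free period 0.5% v 2.9%.

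For the other two items with no change, Weeks 1-5 minus Weeks 1-9 gives +4.2 to +6.4, +3.1 to +6.7, +1.2 to +8.1 and +0.2 to +5.2 points at the four cut-offs. Weeks 2-9 minus Weeks 1-9 stays under 2 points.

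**4. If there is a time trend.** Suppose both arms share a mean change of 0% in Weeks 1-5 and −20% in Weeks 6-9 (assumed). Over Weeks 1-9 placebo then averages (35 × 0 + 28 × (−20))/63 = −8.9%. The 1800 mg/d maintenance item shows −20 − (−8.9) = −11.1 points, and the titration + 1200 mg/d item shows 0 − (−8.9) = +8.9 points, with no drug effect. Here even the mean is shifted.

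**5. Scale.** Cohort 1 has about 46 subjects (protocol synopsis), so 23 per arm. For ≥40% and ≥60% responders with no change, 1.9 to 11.3 points is 0.019 × 23 = 0.4 to 0.113 × 23 = 2.6 subjects. The standard error of a difference in proportions near 30% is √(2 × 0.3 × 0.7/23) = 13.5 points.

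**The case against.** The best defence is that this is a layout choice. Placebo has no dose levels, and SAP sections 9.1 and 9.2 split only the ganaxolone arm by dose, so one full-phase placebo column beside dose-level columns is a possible descriptive format. But the 1200 mg/d maintenance item does not follow that format, no rationale is given, and the choice would still belong in section 10. It would not remove the window-length effect.

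Several limits do stand:

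- The tables are exploratory and descriptive, and the built-in shift is within sampling error for this cohort.
- Every rate and dispersion in the simulation is assumed, and the direction is not uniform. The ≥20% gap can vanish or reverse, and 28-day seizure freedom moves against ganaxolone.
- The longest seizure-free stretch and any 28-day seizure-free period are defined in the SAP over the whole double-blind phase. Section 8.2 applies the outcome measures to the listed periods, but no section redefines these two for a shorter window, so their figures hold only if they are tabulated that way.
- The sentence that excepts the primary endpoint and the 50% responder rate is partly redacted. Whether the unequal windows reach those two cannot be told, and they are not counted here.
- The simulation assumes full follow-up. SAP section 6.3 uses data up to withdrawal, so placebo Weeks 1-9 keeps early withdrawals while ganaxolone Weeks 6-9 holds only subjects who reached Week 6. This further asymmetry is not quantified.

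**Conclusion.** The concern holds, as a minor one. The SAP departs from the protocol in three Cohort 1 comparisons, in both of its lists, without recording or explaining it. The text comparison needs no assumption beyond reading a single week range as applying to both arms, which is its natural sense.

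The effect is largest for 1800 mg/d maintenance, appreciable for titration + 1200 mg/d maintenance, and small for the combined maintenance item. With no change from baseline and no trend, the artefact in the 1800 mg/d item is a few to about 11 points on the ≥40% and ≥60% responder rates, conditional on the assumed rates. Mean changes are unaffected unless there is drift over time. No Cohort 2 primary, key secondary or other test is involved.

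**What to change.** In SAP sections 4.2 and 8.2, identify the items by content and give placebo the same weeks as ganaxolone, as in protocol section 9.7.6:

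- 1200 + 1800 mg/d maintenance: Weeks 2-9 in both arms.
- Titration + 1200 mg/d maintenance: Weeks 1-5 in both arms.
- 1800 mg/d maintenance: Weeks 6-9 in both arms.

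Leave the Weeks 1-9 item and the 1200 mg/d maintenance item as they are. If the full placebo window is also wanted, show it as an additional column, and list and justify it in section 10.

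A cosmetic matter at the same time: the section 4.2 list, as extracted, has two items lettered a and none lettered f, although its lead-in refers to f. Check the source file and re-letter a to f if the fault is real.

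The cost is wording in two lists and the matching table shells, with no new data and no protocol change. Placebo summaries in the three items would rest on 56, 35 or 28 days per subject instead of 63 and so be somewhat noisier. The Weeks 1-9 placebo summary stays visible in the first item.

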8.2.3 Responder Rate

An R% responder is an individual whose reduction of percent change from baseline in seizure frequency is greater than or equal to R%. R% will 20%, 40%, 60%, 80% for one of the secondary points, and 50% for the first key secondary endpoint.

The responder rates between ganaxolone and placebo will be compared using a Logistic Regression Model, with terms for treatment, pooled center (either US or ROW), and baseline 28-day seizure frequency in the model. The test for treatment effect is a test of whether the

coefficient of the treatment term is equal to zero. The number and percentage of responders will be summarized, odds ratio and associated 95% confidence interval and p-values will be reported.

Summary table with descriptive statistics also will be provided in OL phase for both Cohort 1 and Cohort 2, the baseline is the same as for the DB phase.

Summary table of subjects by treatment in each following category for each phase and each cohort will be provided, the cut off of reduction of percent change from baseline will be classified in the following categories: $\leq 0\%$, $\leq 20\%$, $\leq 40\%$, $\leq 60\%$, $\leq 80\%$, and $\leq 100\%$ in the summary table, and the corresponding graph will be displayed also.

8.2.4 Change in the Number of Seizure Free Days per 28-day Period from Baseline

Post-baseline number of seizure free days per 28-day period will be calculated as: (the number of seizure free days in the maintenance treatment period during the double blind phase) divided by the number of days with available seizure data in the treatment phase and multiplied by 28.

Baseline number of seizure free days per 28-day period will be calculated as: the number of seizure free days in the entire baseline phase divided by the number of days with available seizure data in the baseline phase, multiplied by 28.

The calculation of change in number of seizure free days per 28-day period from baseline will be done as follows for each subject:

Post-baseline number of seizure free days per 28-day period – Baseline number of seizure free days per 28-day period.

Change in number of seizure free days between ganaxolone and placebo will be analyzed using a rank ANCOVA, with treatment and pooled center (either US or ROW) as factors and the rank of baseline number of seizure free days per 28-day period as a covariate in the model. The baseline, post-baseline, and change in number of seizure free days per 28-day period from baseline will be summarized by using descriptive statistics. The 95% confidence interval of the median by treatment group will be presented also. The 2-sided significance level of 0.05 will be used for comparison. Hodges–Lehmann estimator of the difference in medians together with 95% confidence interval (CI) will be calculated.

Summary table with descriptive statistics also will be provided in OL phase for both Cohort 1 and Cohort 2, the baseline is same as DB phase.

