4.2 Secondary Efficacy Endpoints

Key Secondary Endpoints:

The 3 key secondary endpoints will be tested using a fixed sequence procedure to protect the familywise error rate at 0.05. If the primary outcome measure is statistically significant, the p-values of the secondary measures will be examined in the order listed below. The process stops at the first p-value above 0.05.

- Responder rate (experiencing a $\geq 50\%$ reduction) during the titration + maintenance treatment periods of the DB phase for Cohort 2
- Change in the number of seizure free days per 28-day period from baseline during the titration + maintenance treatment periods of the DB phase for Cohort 2
- Clinical Global Impression of Change – Improvement (CGI-I; Investigator) at Week 14 of the double blind treatment phase relative to the baseline for Cohort 2

All remaining secondary efficacy endpoints listed in the protocol will be tested at $\alpha = .05$ so all p-values are nominal.

Secondary efficacy outcome measures are listed below.

- a) Percent change in the 28-day seizure frequency from baseline to the DB phase during the maintenance treatment period for Cohort 2
- b) Change from baseline in 28-day seizure frequency during the DB phase for Cohort 2 (titration + maintenance and maintenance only).
- c) Change in the number of seizure free days per 28-day period from baseline during the maintenance treatment period of the DB phase for Cohort 2
- d) Proportion of responders experiencing a $\geq R\%$ reduction from baseline to the end of treatment period in 28-day seizure frequency (titration + maintenance and maintenance only) for Cohort 2. R% will be 20%, 40%, 60%, and 80%
- e) Proportion of subjects who completed the DB portion of the study (Cohort 2) and did not experience any seizures during the maintenance phase of the study
- f) Proportion of subjects who experienced at least one 28-day seizure free period during the DB phase of the study (titration + maintenance) for Cohort 2
- g) Longest period of time seizure free (%) (longest period of seizure free days divided by number of days with available seizure data) during the double blind phase (titration + maintenance) for Cohort 2
- h) Change from baseline in 28-day seizure frequency for different subtypes of seizures during the DB portion of the study (titration + maintenance) for Cohort 2 (SPS, SPS-motor, CPS, SGTC)
- i) Patient Global Impression of Change – Improvement (PGI-I; Patient/Caregiver) at each assessment visit

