5.3 Modified Intent To Treat Population

The modified intent to treat (MITT) population (full analysis population in protocol) includes all randomized subjects who received at least 1 dose of study medication and provided any post baseline seizure outcome data. The MITT population is the primary population for efficacy analysis. Subjects will be analyzed based on their randomized treatment assignment.

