8 EFFICACY

8.1 Primary Efficacy Endpoint and Analysis

The primary efficacy endpoint for US FDA registration is the percent change in 28-day seizure frequency (POS with or without secondary generalization) in Cohort 2 DB phase (14-week titration + maintenance treatment periods) relative to the baseline in the MITTP, frequency of POS seizures only includes 3 seizure subtypes which are SPS-motor, CPS and SGTC. Post-baseline 28-day seizure frequency will be calculated as the number of seizures in the entire treatment phase divided by the number of days with available seizure data in the treatment phase, multiplied by 28. Baseline 28-day seizure frequency will be calculated as the number of seizures in the baseline period divided by the number of days with available seizure data in the baseline period, multiplied by 28. The calculation for percent change from baseline in 28-day seizure frequency will be done as follows for each subject:

$$\left(\frac{[(\text{Post-baseline 28-day seizure frequency}) - (\text{Baseline 28-day seizure frequency})]}{(\text{Baseline 28-day seizure frequency})} \right) \times 100\%$$

The baseline, post-baseline, and percent change from baseline in 28-day seizure frequency will be summarized by treatment group using descriptive statistics.

The null hypothesis is that there is no difference in the medians between the 2 treatment groups with respect to percent change in seizure frequency.

A rank analysis of covariance (ranked ANCOVA) will be used as primary analysis. A nonparametric rank analysis of covariance will be used to analyze rank of percent change data from baseline, with treatment and pooled center (either US or ROW) as factors and the rank of baseline 28-day seizure frequency as a covariate in the model. The baseline, post-baseline, and percent change from baseline in 28-day seizure frequency will be summarized by treatment group by using descriptive statistics. The 2-sided significance level of 0.05 will be used for comparison. Hodges–Lehmann estimator and 95% confidence interval (CI) for the estimator will be calculated.

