An analysis of covariance (ANCOVA) as a sensitivity analysis will be conducted on the rank of percent change data from baseline, with treatment and pooled center (either US or ROW) as factors and the rank of baseline seizure frequency as a covariate. *P*-value to test treatment effect will be determined by permutation test with seed = 123456 and 2000 iterations. To deal with the missing data after subjects dropout, the multiple imputation method described in [Section 6.3](#) will be utilized to perform additional sensitivity analyses. These analyses provide a robustness assessment of the results.

The MITT population of Cohort 2 is the primary population for efficacy analysis. The PP population of Cohort 2 will be considered as supportive.

There are 2 different types of baselines in the study; Cohort 1 has a baseline composed of 4 weeks retrospective + 4 weeks prospective data collection, while subjects in Cohort 2, randomized under protocol amendment 3, has a baseline composed of 8 weeks of prospective data collection; however subjects randomized under protocol amendment 2 will have baseline data that is collected in the same fashion as Cohort 1 subjects. Summary statistics will be generated by type of baseline to provide information regarding the robustness of the endpoint with respect to the choice of baseline. Wilcoxon rank sum test will be used to test if there is difference between these 2 types of baseline. Hodges–Lehmann estimator and 95% confidence interval (CI) for the estimator will be calculated.

For European (EMA) Registration

The primary efficacy endpoint for EMA registration is 50% responder rate during the maintenance treatment phase of DB phase for Cohort 2. A 50% responder is an individual who experiences at least a 50% decrease in seizure frequency compared to baseline. This end-point is analysed independently of the FDA registration end-point, and analysis of the key secondary end-points (below) is not predicated on the results of this end-point.

The responder rates between ganaxolone and placebo will be compared using a logistic regression model, with terms for treatment, pooled center (either US or ROW), and baseline 28-day seizure frequency in the model. The number and percentage of responders will be summarized by treatment, odds ratio and associated 95% confidence interval and p-values will be reported.

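### The only SAP formula for seizure-free days (8.2.4) does not compute the second key secondary endpoint: it counts maintenance days, while the endpoint covers titration + maintenance

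*SAP*

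**What the plan says.** The window of the endpoint is not in dispute. The Protocol (synopsis and 9.7.6) and the SAP (4.2 and 8.2) all place the second key secondary over titration plus maintenance. SAP 4.2 has "Change in the number of seizure free days per 28-day period from baseline during the titration + maintenance treatment periods", and SAP 8.2 has "Change in the number of seizure free days per 28-day period from baseline during the titration + maintenance treatment phases". The maintenance-only version is a separate endpoint, secondary (c), tested at a nominal level: "Change in the number of seizure free days per 28-day period from baseline during the maintenance treatment phase of the DB phase".

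SAP 8.2.4 gives a single post-baseline formula under a heading that names no window. Its core is "seizure free days in the maintenance treatment period during the double blind phase) divided by the number of days with available seizure data"; the full denominator clause reads "divided by the number of days with available seizure data in the treatment phase and multiplied by 28". The baseline formula in the same section uses the baseline phase in both numerator and denominator.

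Protocol 9.5.2 refers the reader to Section 9.7 and the SAP for derivations. Protocol 9.7.6 names the windows but gives no formula for seizure-free days.

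**The concern.** The numerator clearly leaves out the two titration weeks. The denominator term, *treatment phase*, has two fair readings.

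- **Reading 1: the whole 14-week phase.** SAP 8.1 uses the term this way for the primary endpoint: "the number of seizures in the entire treatment phase divided by the number of days with available seizure data in the treatment phase". The 8.2.4 ratio then has mismatched windows.
- **Reading 2: maintenance only.** The SAP also calls maintenance a phase, in the EMA endpoint ("50% responder rate during the maintenance treatment phase of DB phase for Cohort 2") and in secondary (c). The ratio is then coherent, but it is secondary (c), and the key secondary has no formula.

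The endpoint is the second of three steps in a fixed sequence at familywise 0.05, and CGI-I is tested only if it succeeds. On reading 1 the score depends partly on time in study. Early leavers stay in the analysis, because the MITT population needs only that a subject "received at least 1 dose of study medication and provided any post baseline seizure outcome data". On reading 2 an alpha-controlled test would be run on the wrong window.

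**Working it through.** **Inputs from the documents.** Cohort 2 has 14 days of titration and 84 of maintenance, 98 in all (SAP 3.3; Protocol Table 2). The plan has 178 subjects per arm (SAP 3.5) and about 10% discontinuation (SAP 3.4). The test is a rank ANCOVA, two-sided 0.05 (SAP 8.2.4). No power figure is stated for this endpoint, so there is none to reproduce.

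**Formulas.** Let SF be seizure-free days and D days with data, with subscripts T (titration) and M (maintenance).

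- Endpoint as defined: 28 × (SF_T + SF_M) / (D_T + D_M)
- Reading 1: 28 × SF_M / (D_T + D_M)
- Reading 2: 28 × SF_M / D_M

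**Reading 1, completers with an unchanged rate.** The score is multiplied by 84/98 = 0.857. A true 14 becomes 12.0, 20 becomes 17.14 (an apparent change of −2.86), and a fully seizure-free 28 becomes 24.0. A completer must improve by more than 98/84 − 1 = 16.7% to show any gain. A true arm difference of 1.25 days among completers becomes 1.25 × 0.857 = 1.07.

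**Reading 1, leavers with an unchanged rate and a complete diary.** The fraction kept on leaving at day d is max(0, d − 14)/d.

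| Exit day | Fraction kept | Apparent change if baseline is 20 (true change 0) |
|---|---|---|
| 14 | 0 | −20.00 |
| 21 | 0.333 | −13.33 |
| 28 | 0.50 | −10.00 |
| 56 | 0.75 | −5.00 |
| 98 | 0.857 | −2.86 |

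**Reading 2.** Assume 20 seizure-free days per 28 at baseline, 16 in titration and 22 in maintenance. The endpoint as defined is (16 × 14 + 22 × 84)/98 = 21.14, a change of +1.14. Reading 2 gives 22 − 20 = +2.00. Reading 1 gives 22 × 84/98 − 20 = −1.14. On reading 2, a subject who leaves during titration is 0/0 and has no value.

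**Illustration of the effect on the test, reading 1.** The documents give no distribution for seizure-free days and no dropout split or timing for this trial. The assumptions are: baseline mean 18 and SD 4, change noise SD 4, true gain 1.25 or 0, 178 per arm, and exit day uniform on 1–97 (even) or 1–28 (early). The model is the rank ANCOVA with treatment, two-level centre and ranked baseline, with 3000 replicates. Power with the correct formula is 79–83% throughout.

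| Dropout, ganaxolone v placebo | Power as written, even / early | False rejection as written, even / early |
|---|---|---|
| 0% v 0% | 81% / 81% | 5.6% / 4.7% |
| 10% v 10% (planned overall rate) | 75% / 65% | 5.1% / 4.7% |
| 7.1% v 6.1% | 72% / 66% | 4.9% / 5.7% |
| 15% v 8% (assumed imbalance) | 52% / 20% | 8.9% / 19.5% |

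The 7.1% and 6.1% are adverse-event discontinuations in Study 1042-0600 (Protocol 7), the only by-arm rates in the documents. The two 0% entries differ only by simulation error.

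The direction follows the imbalance. At 15% v 8%, about 8% / 19% of null trials reject in favour of placebo and about 0.3% / 0.1% in favour of ganaxolone, against a nominal 2.5% on each side. With the imbalance reversed, about 9% / 18% reject in favour of ganaxolone.

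**The case against.** The strongest reply is that the endpoint itself is settled. Its window is stated the same way four times, and 8.2.4 looks like a block completed for secondary (c) and meant to serve both endpoints. A careful programmer could follow the definition in 8.2. That is true, and it makes this a derivation error and not a dispute over the endpoint. But the programmer would have to override the one written formula, and doing so after unblinding would look like a post hoc change to an alpha-controlled test.

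Second, all the quantified harm sits on reading 1, the less coherent reading, since the SAP matches its windows elsewhere (8.1, 8.2.6). This stands as a limit: on reading 2 neither the deflation nor the loss of power arises. Reading 2 still yields the wrong endpoint.

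Third, the power figures are not trial figures. Gain, SD and baseline are each assumed at a single value, and the largest losses need early exits or an invented 15% v 8% split. With more dropout on ganaxolone the formula works against the drug; a false efficacy claim needs excess placebo dropout, for which the documents give no evidence. This also stands, and the figures should be read as illustration only.

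Fourth, parts of the SAP are absent from the public copy and the mock-ups are in a separate file, so a correct formula elsewhere cannot be excluded. Nothing in the available text suggests that one exists.

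**Conclusion.** The concern holds. As written, SAP 8.2.4 does not return the second key secondary endpoint on either reading of its denominator.

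The certain part is arithmetic: on reading 1 unchanged completers keep 0.857 of their score, and unchanged leavers keep between 0 and 0.857 depending on exit day. Deflation common to completers in both arms hardly alters the test, but it distorts the reported change and shrinks the estimated difference. The loss of power comes from early leavers. On the assumptions stated, it is from about 81% to 75% / 65% at 10% dropout in both arms. The false rejection rate stays at about 5–6% unless dropout differs between arms, and the bias then runs against the arm with more dropout.

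The exposure is limited to steps 2 and 3 of the key secondary sequence, and only if the primary and the first key secondary succeed. This formula does not touch the FDA primary, the EMA endpoint or the first key secondary. It must still be corrected before database lock, because an alpha-controlled step has no derivation that yields it.

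**What to change.** Replace the single post-baseline formula in SAP 8.2.4 with two:

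- **Key secondary:** seizure-free days in titration + maintenance, divided by days with available seizure data in titration + maintenance, times 28.
- **Secondary (c):** seizure-free days in maintenance, divided by days with available seizure data in maintenance, times 28.

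Add that MITT subjects with no maintenance diary days have no value for (c), are left out of that nominal test in line with the SAP 6.3 rule of not imputing missing days, and are counted by arm. Use one term for each window throughout SAP 8.2, so that *treatment phase* no longer carries two meanings.

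The cost is three or four lines of SAP text before database lock. No new data are needed, and the choice of window is not reopened.
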